4.5.7. Adverse Events Monitoring

Please refer to Section 4.4.7.

4.5.8. Data Collection, Management, Analysis, and Monitoring

4.5.8.1. Data Collection Overview

Delivery trial data will be collected electronically and on paper as described below.

4.5.8.2. Measurement of Implementation Outcomes

In the Delivery Trial, existing community health workers will be trained to distribute azithromycin to children 1–59 months of age or 1–11 months of age every 6 months. In communities randomized to fixed-point delivery, community health workers (CHWs) will work with community leaders to identify a central location, date, and time for delivery. Mobilizers in each community will be engaged to publicize the intervention. In communities randomized to door-to-door delivery, CHWs will visit every household in the community. In both sets of communities, CHWs will determine eligibility, obtain informed consent, administer treatment, and record treatment administration on paper data collection forms. For eligible children in Delivery Trial I, the dose will be determined via weight using a hanging scale for children under 12 months of age or height-stick approximation for children 12 months and older using the Niger trachoma program's height stick. For eligible children in Delivery Trial II, the dose will be determined via age for children under 6 months of age or height-stick approximation for children 6 months and older using the Niger trachoma program's height stick. Treatment coverage will be monitored by tracking the total number of children treated in each community as recorded by CHWs during distributions. Denominators for treatment coverage will be estimated through a post-distribution census conducted by trained census workers.

Program costs

Program costs will be captured through micro-costing (units of resources used multiplied by the

unit costs thereof). The economic approach will assign value to all items used, regardless of the payer, and regardless of whether the resources consumed are fully monetized. A macro-costing approach will be used for reconciliation and for understanding cost efficiency: overall program spending and outputs will be compared to the totals found via micro-costing. Costs will be collected using both routine project administrative data collected for all study communities (e.g., expenditure reports for services delivered, operational reports for distances travelled) with “program costs” being defined as costs needed to deliver the program in the absence of any research efforts. Research costs will be measured as part of the overall project but removed when comparing different age and delivery options to more accurately reflect an azithromycin MDA program. The *micro* and *macro* approaches are described in turn below. Finally, ‘start-up’ costs will be distinguished from ongoing running costs.

In addition to routine project administrative data collection, targeted additional data collection in the form of time and motion (T&M) studies for a small subset of communities will be implemented. As described below, the T&M studies will adapt and use forms that have been successfully used in other studies. Forms and data entry and analysis systems needed for routine program accounting, management and reporting purposes will be developed concurrently with the cost data collection needed for economic analysis and piloted using pre-implementation expenditures.

Program micro-costing

Cost information collected through regular project records will include the following categories:

- **Personnel:** Salaries and benefits (and any other emoluments, such as bonuses, etc.) for all staff, including service delivery (azithromycin distribution), program administration, transportation, etc.
- **Consumables:** Medications, office supplies, dosing cups, syringes, water, scales, height sticks, fuel, and supplies needed for AMR surveillance, including swabs, tubes, media, storage, shipment, and processing, etc.
- **Services:** Transportation, equipment maintenance, utilities, publicity, transport.
- **Equipment:** Vehicles, laboratory equipment, and other significant capital items.
- **Training:** Salaries, per diems, transport, food, etc.
- **Space:** Rental cost and/or purchase depreciation.

The last three items, equipment, training, and space will be appropriately amortized.

Costs will be allocated appropriately in collaboration with local project staff in order to ensure accurate division of project and research costs. Should the economics team find discrepancies, in whether a cost is research or project oriented, the team alongside local project staff will discuss until consensus is achieved. Services-related, non-research costs will then be allocated to the categories listed above and cross-categorized by particular activities. These activities include direct service delivery excluding supervision; field supervision; transportation, and overhead, among others. Expenditure data will be allocated to these activities by recall via structured interviews and, for a small subset of sites, via T&M data. These costs can then be allocated to the community level according to a schema consistent with the one developed for the provisional cost model and which reflects current budget items. Cost allocation will distinguish payer (government / program, volunteer/contributed) and location (community, district, region).

Time & Motion (T&M) studies

T&M will be conducted at least twice per region and distribution, for one week each time, for a sample of communities. The T&M activity has three purposes. First, it is one of the approaches we will use to compare the resources needed at the community level between the 1 – 11 month and 1 – 59-month distribution strategies and the fixed-point versus door-to-door strategies in the Delivery Trial. Second, the T&M data will inform modeling of intervention cost in settings with different characteristics. Third, the T&M data will help to disaggregate field costs associated with delivery of a real-world intervention from those related to the research setting. The T&M will quantify:

- Time spent on program activities vs. other responsibilities (if any).
- Within program activities, time spent at the community level (e.g. with a local leader), moving around the community, addressing household-level issues such as explanation and consent, and administering azithromycin to individual children.
- At both the community and the household level it will allow us to distinguish between fixed and variable costs.

Sampling for T&M will be conducted in order to provide robust estimates for important subgroups, including geographic regions, village size, difficult-to-reach villages, and other factors to be decided.

Cost Differentiation

Start-up costs. Large expenditures often occur in the early phases of a project when sizable one-time costs are incurred. This includes vehicle purchases, other equipment, and furniture purchases, building refurbishment, and some training costs.

Focus on items contributing to majority of costs. Previous experience suggests that total costs are disproportionately attributable to a relatively small number of items. Data collection will therefore be calibrated via a formal “forest and trees” process of identifying the limited number of inputs constituting 90 - 95% of costs. We will reduce efforts to obtain high precision for items comprising the other 5 - 10%.

Tracking costs over time. Unit costs may vary over time. For example, both administrative and field teams may become more efficient as they gain experience. We will generate graphs which display trends in major cost categories over time. We will also conduct structured interviews that aim to identify the proximate causes for observed changes in efficiency.

Program macro-costing

After removing research-related costs, program costs will be divided by the total number of outputs to arrive at a set of unit cost estimates. If these approximate the array of unit cost estimates obtained from the micro-costing approach described above, this would reconcile the micro-costing approach.

Cost-effectiveness analyses

Program costs and mortality outcomes will be used to develop incremental cost-effectiveness ratios (ICERs) for age group comparisons as detailed in the SAP.

Table 3 summarizes the collection of additional process indicators to track key implementation

outcomes using the Proctor Implementation Outcomes and RE-AIM frameworks, which will be applied across work streams for program monitoring and evaluation.

Table 3. Proctor Implementation Outcomes and RE-AIM Frameworks Applied to AVENIR

Outcome	Definitions	Sources of Data
Acceptability/Appropriateness	Perception of and satisfaction with intervention, facilitators and barriers to participation and implementation, relevance of intervention; at participant/community, implementer, and governmental levels	Semi-structured interviews, surveys
Reach/Penetration	Census coverage Refusals and reasons for refusals Treatment coverage, equity of coverage by sex, age, geography	Census, NSVRS Census, administrative data Census
Cost	Program costs Cost-effectiveness	Administrative data, micro-costing Administrative data, census, micro-costing
Feasibility/Fidelity	Timeliness and fidelity of intervention rollout Training and supervision metrics, staff retention Drug storage, temperature, inventory, delivery monitoring AMR sample viability, rejection rates, processing speed	Administrative data, site visits Administrative data, site visits Administrative data Administrative data
Sustainability	Above metrics compared over time	See above

4.5.8.3. Data Collection and Management

Please refer to section 4.4.8.5.

4.5.8.4. Statistical Analysis Plan

Please refer to section 4.4.8.6.

4.5.8.5. Quality Control and Monitoring

Please refer to section 4.4.8.7.

4.6. Programmatic Trial

4.6.1. Trial Design

The remaining 1,500 eligible communities will participate in a Programmatic Trial that utilizes existing community health workers working with the Niger Ministry of Health community health program. The distribution of biannual azithromycin will begin approximately 1.5 years after the first Mortality Trial enrollment and will be offered to children aged 1–11 months in selected CSIs. CSIs will be used as the randomization unit. CSIs will be randomized in a 2:1 allocation to azithromycin distribution to children aged 1–11 months by community health workers or no azithromycin distribution / usual care by community health care workers, with the allocation favoring azithromycin. AMR after 1 year will be monitored at the community level using similar methods to the Mortality/Resistance Trial as well as in children presenting to selected CSIs with diarrheal disease, respiratory infection, or for a well-child visit. Mortality will be monitored by birth histories after 2 years of treatment distribution.

After 1 year of distributions, the results from the Mortality/Resistance trial will be available and will be used to inform the next steps for the Programmatic Trial. The trial may continue based on the Mortality trial results, the availability of funding, and stakeholder preferences. If the study continues, additional regions will be included in the Programmatic Trial (Figure 2), using adaptive randomization as described for the Mortality/Resistance Trial. The original Mortality/Resistance Trial communities would also be included in the Programmatic Trial during this expansion. Mortality, resistance, and clinic visits will be monitored every 2 years. In this platform trial, additional treatment arms may be added to the trial or arms may be dropped from the trial based on additional information from other studies, updates to the WHO guidelines, and preferences from programs and policymakers in Niger. With such changes, protocol details, power calculations, and analysis plans will be updated accordingly in the protocol and statistical analysis plan.

4.6.2. Eligibility

Intervention

At the CSI-level, eligibility includes*:

Inclusion criteria:

- Location in Dosso, Tahoua, Maradi, Zinder, or Tillabéri regions
- Verbal consent of community leader(s)

Exclusion criteria:

- Inaccessible or unsafe for study team
- “Quartier” designation on national census

* Community-level eligibility for the programmatic trial will be based on Ministry of Health community health worker program guidelines and may change from what is currently listed above.

At the individual-level, eligibility includes:

Inclusion criteria:

- Age 1–11 months
- Primary residence in a study CSI
- Verbal consent of caregiver/guardian for study participation

Exclusion criteria:

- Known allergy to macrolides

Population-based sample collections

At the community-level, eligibility includes:

Inclusion criteria:

- Location in study region
- Distinguishable from neighboring communities
- Verbal consent of community leader(s)

Exclusion criteria:

- Inaccessible or unsafe for study team
- Not randomly selected
- Received treatment prior to sample collection

At the individual-level, eligibility includes:

Inclusion criteria:

- Age 1–59 months
- Primary residence in a study community selected for sample collections
- Written consent of caregiver/guardian for study participation

Exclusion criteria:

- Not on list of randomly selected participants from the census

CSI-based sample collections

At the CSI-level, eligibility includes*:

Inclusion criteria:

- Randomly selected CSI for inclusion within the Programmatic Trial
- Verbal consent of CSI leader(s)

Exclusion criteria:

- Not randomly selected for participation in the Programmatic Trial

*CSI-level eligibility for the programmatic trial will be based on Ministry of Health community health worker program guidelines and may change from what is currently listed above.

At the individual-level, eligibility includes:

Inclusion criteria:

- Presents to CSI with symptoms of diarrheal disease, respiratory illness, or visiting for routine healthcare (e.g. vaccination)
- Verbal consent of caregiver/guardian for study participation

Exclusion criteria:

- Presents to CSI with disease symptoms not related to diarrheal or respiratory disease
Received study treatment prior to sample collection

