4.6.3. Randomization, Adaptation, and Masking

4.6.3.1. Randomization

The randomization unit for these trials will be the CSI. Each CSI includes a catchment area of approximately 10 communities.

CSIs will be randomized in a 2:1 allocation favoring azithromycin to the following 2 arms:

- **Programmatic azithro 1–11:** all children aged 1–11 months will be offered a biannual dose of azithromycin. This distribution will be provided by existing community health workers as part of the Ministry of Health's community health program.
- **Programmatic no intervention:** All children aged 1–11 months will not receive azithromycin within the framework of this study. However, all children in this study will receive other health services provided by community health workers as part of the Ministry of Health's community health program.

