4.6.3.3. Masking

In the Programmatic Trial, participants, and implementers will not be actively masked from the study arm allocation given that no placebo will be used. Outcome assessors and data analysts will be masked.

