4.6.4.2. Secondary Outcomes

- Prevalence of genetic determinants of macrolide resistance in nasopharyngeal swabs in children aged 1–59 months from population-based samples after 2 years of distribution
- Load of genetic determinants of macrolide resistance in rectal swabs among children aged 1–59 months from population-based samples after 2 years of distribution
- Prevalence of genetic determinants of macrolide resistance in nasopharyngeal swabs in children aged 1–59 months with respiratory illness from CSI-based samples after 2 years of distribution
- Load of genetic determinants of macrolide resistance in rectal swabs among children aged 1–59 months with diarrheal disease from CSI-based samples after 2 years of distribution
- Infant- and under-5 mortality rate (deaths per 1,000 livebirths) 2 years after the first treatment as assessed via birth history

Program costs as captured by routine administrative data collection during the study period and by micro-costing activities

- Estimated national-scale effects (health and cost) of scaling up each strategy. Other implementation outcomes defined in the Proctor Outcomes Framework,¹³ including feasibility and acceptability, as captured during routine administrative and monitoring data collection during the study period and by stakeholder interviews at the participant, community, and health system levels after one round of distributions (Table 3)
- Treatment coverage as defined by projections using national and study census data collection as well as satellite imagery

Microbiome outcomes for rectal swab collections

- Gamma diversity, estimated as the alpha diversity of the pooled community sample using the Shannon diversity index
- Overall microbial structure using Manhattan distance
- Relative abundance of individual microbial taxa at genus and species level

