4.6.8.3. Measurement of Sample Based Outcomes

In the Programmatic Trial, sample collection will take place within communities in the catchment area of 40 selected CSIs (20 CSIs per arm) and at the same 40 selected CSI locations.

- For samples collected within communities (population-based):
 - 3 communities per CSI from each of the 40 CSIs (120 communities total) will be randomly selected from the pool of eligible communities and followed to monitor antimicrobial resistance. In each community, 10 children aged 1–59 months will be selected to participate in nasopharyngeal and rectal swab sample collections. One rectal swab and one NP swab will be collected from each child.
- For samples collected at CSI locations (CSI-based):
 - 1 rectal swab will be collected from the first 30 children who present to the CSI with symptoms of diarrheal disease.
 - 2 nasopharyngeal swabs will be collected from the first 30 children who present to the CSI with symptoms of respiratory disease. The second nasopharyngeal swab collected will be sent to the CERMES lab for processing.

- 1 rectal swab and 2 nasopharyngeal swabs will be collected from the first 30 children who for routine medical care (e.g. vaccination) and present with no disease symptoms. The second nasopharyngeal swab collected will be sent to the CERMES lab for processing.

In the Programmatic Trial, population-based sample collections will follow similar procedures to those described above for the Mortality/Resistance Trial. CSI-based collections will take place in the same month as the community-based collections for that CSI, with a window of + or – 1 month. The presence of diarrheal or respiratory illness will be determined using the UNICEF Integrated Management of Childhood Illness flowchart currently used in Niger. Eligible children will be consecutively enrolled until the target sample sizes are achieved. A copy of the Integrated Management of Childhood Illness flowchart that will be used can be found in the Section 7.12 of the appendix.

To randomly select individuals for population-based monitoring in the Programmatic Trial, a “random walk” approach will be used.

Random walk selection protocol

1. Start at the home of the chef du village.
2. Use the application in CommCare to determine how many steps to go and in which direction to walk.
3. Approach the household that is closest to you when you finish your steps.

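### The exclusion of treated children from clinic-based resistance sampling has no time window and acts almost only in the azithromycin arm

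*Protocol*

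**What the plan says.** The individual-level exclusions for CSI-based sampling in Protocol 4.6.2 include "Received study treatment prior to sample collection". Neither that line nor the text around it gives a round or an interval.

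Protocol 4.6.3.1 defines the arms. In one, "all children aged 1–11 months will be offered a biannual dose of azithromycin". In the other, "All children aged 1–11 months will not receive azithromycin within the framework of this study". Protocol 4.6.3.3 adds that participants and implementers "will not be actively masked from the study arm allocation given that no placebo will be used".

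The outcomes concerned are secondary (Protocol 4.6.4.2). They are prevalence of macrolide-resistance determinants in nasopharyngeal swabs from children "with respiratory illness from CSI-based samples after 2 years of distribution", and load in rectal swabs from children "with diarrheal disease from CSI-based samples after 2 years of distribution". Section 4.6.1 also mentions resistance monitoring at CSIs after 1 year.

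On timing, Protocol 4.6.8.3 says "CSI-based collections will take place in the same month as the community-based collections for that CSI", and allows 1 month either side. Section 4.6.5.2 holds back a round's treatment until sampling is done, but only in the communities chosen for sampling.

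**The concern.** The exclusion depends on exposure after randomization, and that exposure exists in only one arm. Applied as written, it compares untreated children in azithromycin CSIs with all children in control CSIs. The stated outcome covers children 1–59 months old after 2 years of distribution, with no restriction to untreated children.

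The distortion would be hard to see in the data. Section 4.6.8.3 enrols consecutive attenders until 30 per presentation group are reached, so each excluded child is replaced by an untreated one. The sample size stays full and nothing appears as missing.

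Two effects follow. If dosed children carry more resistance than undosed children in the same arm, the arm difference shrinks. The age mix of the two arms also diverges. At stake is whether the clinic-based results can be read as the effect of the programme on resistance in sick children.

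**Working it through.** **No stated figure to reproduce.** The supplied documents give no power or sample-size calculation for this comparison, and the SAP overview leaves the Programmatic Trial to a separate SAP. The formula in step 5 was first checked on the nearest stated figure, nasopharyngeal prevalence in SAP 3.2.3. With 50 × 30 = 1,500 children per arm, the effective size is 1,500 / (1 + 29 × 0.045) = 651. For 30% against 38% at two-sided alpha 0.025, power is 79.0% (85.4% against 22%). The SAP says at least 80%.

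**Step 1: who can meet the criterion.** In the azithromycin arm, any child dosed at 1–11 months. In the control arm, nobody, apart from a treated child who moved in from another catchment.

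**Step 2: literal reading (ever treated).** Assume uniform ages over 1 to under 60 months (59 months) and dosing at 1 to under 12 months of age (11 months). With doses 6, 12, 18 and 24 months before sampling, those dosed are now aged 7–17, 13–23, 19–29 and 25–35 months. The union is 7–35 months, or 29 of 59 month-ages. Of these, 15 had two dosing opportunities and 14 had one.

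- Full coverage: 29/59 = 49%.
- 80% of the band ever treated: 0.8 × 29/59 = 39%.
- 80% per dose, doses independent: (14 × 0.80 + 15 × 0.96)/59 = 25.6/59 = 43%.

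After two distributions the band is 7–23 months (17 month-ages, 5 of them with two opportunities). The matching figures are 29%, 23% and 24%.

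**Step 3: narrow reading (treated in this round).** At most the 11 month-ages just dosed: 11/59 = 19%, or 15% at 80% coverage.

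| Share of azithromycin arm excluded (per-dose coverage) | 100% | 80% | 60% |
|---|---|---|---|
| Ever treated, four distributions | 49% | 43% | 36% |
| Ever treated, two distributions | 29% | 24% | 19% |
| This round only, maximum | 19% | 15% | 11% |
| Control arm | about 0% | about 0% | about 0% |

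Coverage is an assumption throughout. The narrow figure falls to near 0 if clinic sampling precedes dosing in the whole catchment. The protocol does not secure that order. The hold covers 3 sampled communities of about 10 per CSI, and the window lets clinic sampling run up to 1 month after community sampling.

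**Step 4: dilution.** Let f be the treated share of the azithromycin arm, T the effect in treated children and sT the effect in untreated children. With everyone kept, the arm difference is T[f + (1 − f)s]. With treated children removed it is sT. The share retained is s / [f + (1 − f)s].

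| s | 0 | 0.25 | 0.5 | 0.75 | 1 |
|---|---|---|---|---|---|
| f = 0.49 | 0% | 40% | 67% | 86% | 100% |
| f = 0.43 | 0% | 44% | 70% | 87% | 100% |
| f = 0.15 | 0% | 69% | 87% | 95% | 100% |

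In the last row, s compares children not dosed this round with those dosed this round. A value near 0 is less likely there, because children dosed in earlier rounds stay in the sample. The documents do not give s.

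**Step 5: power illustration.** Inputs are 20 CSIs × 30 children per arm for one presentation group (Protocol 4.6.8.3), with 30% prevalence and ICC 0.045 borrowed from SAP 3.2.3, and two-sided alpha 0.05. The effective size is 600 / 2.305 = 260 per arm. A 12-point difference has 82% power with treated children kept. With f = 0.49 removed:

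| s | Difference (points) | Power |
|---|---|---|
| 0.75 | 10.3 | 69% |
| 0.5 | about 8 | 49% |
| 0.25 | 4.9 | 22% |
| 0 | 0 | 5% |

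**The case against.** The strongest reply is that the line means treated in this round. The population-based rules carry a near-identical exclusion at community level. Read literally, that rule would remove every treated community after 2 years and leave nothing to compare, so the authors cannot have meant it. The revision history describes the Mortality Trial's community-level rule as round-specific, and Protocol 4.6.5.2 and 4.6.8.3 place dosing after sampling. Not sampling a child dosed days earlier would be a reasonable aim.

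This stands as the likely intent, and it cuts the loss to the third row of the first table. It does not settle the matter. No current wording limits the clinic criterion to a round. The revision-history entry dates from May 2021, before clinic-based sampling was added in April 2022. Under the narrow reading any removal is still one-sided.

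A reader might also infer that the Programmatic Trial's resistance comparison as a whole is biased to the null and that a null result would be worthless as safety evidence. The documents do not support that. Population-based nasopharyngeal and rectal outcomes are listed separately, and their individual-level criteria contain no treatment exclusion. Nor is dilution certain: if untreated children in treated catchments carry the same excess resistance (s = 1), the treatment-related difference is fully retained.

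The separate Programmatic SAP and the sample-collection procedures were not available and may define a window. Eligibility is nevertheless set in the protocol.

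**Conclusion.** The concern holds for the clinic-based secondary resistance outcomes, and for the microbiome outcomes in so far as they use clinic rectal swabs. The exclusion has no window and falls almost exclusively on the azithromycin arm under either reading.

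Its size depends on the reading. Ever treated means about 39–43% of otherwise eligible children after four distributions, and 23–24% after two. Treated in this round means at most about 15%, and possibly near 0. These figures assume 80% coverage and uniform ages. Actual clinic attenders, some of them coming for vaccination, may have a different age distribution.

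The pull is toward no difference only to the extent that treated children carry more resistance than untreated children in the same arm. That fits the direction the protocol hypothesizes for the Mortality/Resistance Trial (Specific Aim 2). The change in age mix adds a further effect of unknown direction, because the documents give no age-specific resistance.

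**What to change.** - Delete the individual-level treatment exclusion from the CSI-based sampling criteria in Protocol 4.6.2. If a current-round rule is intended, say so in the criterion.
- Require clinic samples to be collected before that round's distribution anywhere in the CSI catchment, not only in the three sampled communities. Use a calendar-matched window in control CSIs.
- Record prior study treatment as a descriptive variable, so that results can be shown by treatment history without selecting on it.

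This needs a wording change in 4.6.2 and a tighter timing rule in 4.6.8.3. It constrains the sampling dates and leaves dosing and sample size alone. The downside is a narrower clinic sampling window relative to distribution, which may make it harder to reach 30 consecutive children per presentation group.
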